9.9 Adverse Event Occurring Secondary to Other Events

In general, AEs occurring secondary to other events (eg, cascade events or clinical sequelae) should be identified by their primary cause. For example, if severe diarrhea is known to have resulted in dehydration, it is sufficient to record only diarrhea as an AE or SAE on the CRF.

However, medically significant AEs occurring secondary to an initiating event that are separated from the initiating event in time should be recorded as independent events on the CRF. For example, if a severe gastrointestinal hemorrhage leads to renal failure, both events should be recorded separately on the CRF.

9.10 Persistent or Recurrent Adverse Events

A persistent AE is one that extends continuously, without resolution between patient evaluation time points. Such events should only be recorded once in the CRF unless their severity increases. If a persistent AE becomes more severe, it should be recorded again on an AE/SAE CRF.

A recurrent AE is one that occurs and resolves between patient evaluation time points and subsequently recurs. All recurrent AEs should be recorded on an AE/SAE CRF.

9.11 Abnormal Laboratory Values

Only clinically significant laboratory abnormalities that require active management will be recorded as AEs or SAEs on the CRF (eg, abnormalities that require study drug dose modification, discontinuation of study drug, more frequent follow-up assessments, further diagnostic investigation, etc).

If the clinically significant laboratory abnormality is a sign of a disease or syndrome (eg, alkaline phosphatase and bilirubin $5 \times$ ULN associated with cholecystitis), only the diagnosis (eg, cholecystitis) needs to be recorded on the AE/SAE CRF.

If the clinically significant laboratory abnormality is not a sign of a disease or syndrome, the abnormality itself should be recorded as an AE or SAE on the CRF. If the laboratory abnormality can be characterized by a precise clinical term, the clinical term should be recorded as the AE or SAE. For example, an elevated serum potassium level of 7.0 mmol/L should be recorded as “hyperkalemia.”

Observations of the same clinically significant laboratory abnormality from visit to visit should not be repeatedly recorded as AEs or SAEs on the CRF, unless their severity, seriousness, or etiology changes.

9.12 Death

All deaths that occur during the protocol-specified AE reporting period, regardless of attribution, should be recorded on an AE/SAE CRF and expeditiously reported to the sponsor or its designee. This includes death attributed to tumor progression.

When recording a death event, the underlying condition that caused or primarily contributed to the fatal outcome should be reported as AE and death being the outcome of the event on the AE/SAE CRF. If the primary cause of death is unknown and cannot be ascertained at the time of reporting, record “Unknown Death” on the AE/SAE CRF.

If the death is attributed to progression of cancer, record “Cancer Progression” as the AE term on the CRF.

9.13 Previously Existing Medical Condition

A preexisting medical condition is one that is present at the start of the study. Such conditions should be recorded on the Medical and Surgical History CRF.

A preexisting medical condition should be recorded as an AE or SAE only if the frequency, severity, or character of the condition worsens during the study. When recording such events on an AE/SAE CRF, it is important to convey the concept that the preexisting condition has changed by including applicable descriptors (eg, “more frequent headaches”).

9.14 Hospitalization, Prolonged Hospitalization, or Surgery

Any AE that results in hospitalization or prolonged hospitalization should be documented and reported as an SAE unless specifically instructed otherwise in this protocol.

There are some hospitalization scenarios that do not require reporting as an SAE when there is no occurrence of an AE. These scenarios include a planned hospitalization or prolonged hospitalization to:

- Perform an efficacy measurement for the study
- Undergo a diagnostic or elective surgical procedure for a preexisting medical condition that has not changed
- Receive scheduled therapy for the target disease of the study

9.15 Pregnancy

A female patient must be instructed to stop taking the study medication and immediately inform the investigator if she becomes pregnant during the study. The investigator should report all pregnancies within 24 hours to the sponsor or its designee. The investigator should counsel the patient; discuss the risks of continuing with the pregnancy and the possible effects on the fetus. Monitoring of the patient should continue until conclusion of the pregnancy. Pregnancies occurring up to 30 days after the completion of the study medication must also be reported to the investigator.

Abortion, whether therapeutic or spontaneous, should always be classified as serious (as the Sponsor considers these medically significant), recorded on an AE/SAE CRF, and expeditiously reported to sponsor its designee.

Any congenital anomaly/birth defect in a child born to a female patient or female partner of a male patient exposed to the investigational product should be recorded and reported as an SAE.

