in the dose expansion phase, in such cases both the targeted therapy (everolimus and sunitinib) and the SSA must be discontinued at least 4 weeks before the first dose of study drug.

7. Patients must have measurable disease (according to RECIST Version 1.1);
8. Patients must have radiological documentation of progression of disease in the last 12 months prior to the initiation of study drug;
9. ECOG performance status of 0 or 1;
10. Expected survival of more than 12 weeks;
11. For female patients of childbearing potential and male patients with partners of childbearing potential, agreement (by patient and partner) to use a highly effective form(s) of contraception, that results in a low failure rate (<1% per year) when used consistently and correctly, starting during the screening period, continuing throughout the entire study period, and for 90 days after taking the last dose of study drug. Such methods include: oral hormonal contraception (combined estrogen/progestogen, or progestogen-only), associated with inhibition of ovulation together with another additional barrier method (e.g., diaphragm, always containing a spermicide), intrauterine device (IUD), intrauterine hormone-releasing system (IUS), bilateral tubal ligation, vasectomized partner (on the understanding that this is the only one partner during the whole study duration), or sexual abstinence. Oral contraception should always be combined with an additional contraceptive method (i.e., barrier method) because of a potential interaction with the study drug. The same rules are valid for male patients involved in this clinical trial if they have a partner of childbearing potential. Male patients must always use a condom. A woman is considered to be of childbearing potential if she is postmenarcheal, has not reached a postmenopausal state (ie, ≥ 12 continuous months of amenorrhea with no identified cause other than menopause), and has not undergone surgical sterilization (removal of the ovaries and/or uterus).

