8.1.3 Laboratory Test Evaluations

Samples for hematology, serum chemistry, urinalysis and pregnancy testing will be analyzed at the study site's local laboratory. Laboratory assessments will include the following:

Hematology: complete blood count [CBC], including red blood cell [RBC] count, hemoglobin, hematocrit, white blood cell [WBC] count with differential [neutrophils, eosinophils, lymphocytes, monocytes, basophils, and other cells], and platelet count), INR, PT and aPTT.

Serum chemistry: blood urea nitrogen [BUN], creatinine, sodium, potassium, chloride, bicarbonate, calcium, magnesium, phosphate, glucose, total bilirubin, direct bilirubin, ALT, AST, alkaline phosphatase, lactic dehydrogenase [LDH], amylase, total cholesterol, triglycerides, total protein, albumin, and uric acid.

Serum pregnancy test at screening and within 30 days after treatment completion for all women of childbearing potential, including those who have had a tubal ligation. In

addition, urine pregnancy tests will be performed on Day 1 of Cycle 2, and continue on Day 1 at each 28-day cycle thereafter.

Urinalysis (pH, glucose, protein, and blood); if there is $\geq 2+$ protein on urinalysis, then a 24-hour urine protein should be done within in one week. For urinalysis results conversions, please refer to Appendix H

Thyroid function: TSH, free T3, free T4 ;

Stool blood test (as per the institutions standard practice);

Plasma surufatinib concentrations (for PK evaluations) will be assessed using a validated assay.

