9.3 Adverse Events Reporting Period

After informed consent, but prior to initiation of study medications, only SAEs caused by a protocol-mandated intervention will be collected (eg, SAEs related to invasive procedures such as biopsies, medication washout, or no treatment run-in).

After initiation of study medications, all AEs and SAEs regardless of attribution will be collected until 30 days following the last administration of study drug or study discontinuation/termination, whichever is later. After this period, investigators should report only SAEs that are felt to be related to prior study drug.

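### Contraception is required for 90 days after the last dose but pregnancies are expressly reportable only to day 30, so for days 31–90 nothing clearly requires a pregnancy to be reported as such.

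*Protocol*

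**What the plan says.** **Contraception.** Protocol 6.1, inclusion criterion 11, asks for highly effective contraception from screening, "continuing throughout the entire study period, and for 90 days after taking the last dose of study drug". It applies to women who could become pregnant and extends to men: "The same rules are valid for male patients involved in this clinical trial if they have a partner of childbearing potential".

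**Pregnancy reporting.** Protocol 9.15 first tells a female patient who becomes pregnant on study to stop study drug and inform the investigator. It continues: "The investigator should report all pregnancies within 24 hours to the sponsor or its designee". It then asks that she be monitored until the pregnancy ends, and adds: "Pregnancies occurring up to 30 days after the completion of the study medication must also be reported to the investigator".

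**Testing.** Protocol 8.1.3 places the last test shortly after treatment: "Serum pregnancy test at screening and within 30 days after treatment completion for all women of childbearing potential".

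**General safety collection.** Under Protocol 9.3, adverse events "will be collected until 30 days following the last administration of study drug or study discontinuation/termination, whichever is later". The section then says: "After this period, investigators should report only SAEs that are felt to be related to prior study drug".

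**Late outcomes.** Protocol 9.15 makes reportable as serious "Any congenital anomaly/birth defect in a child born to a female patient or female partner of a male patient exposed to the investigational product". Protocol 9.20 asks for notification if the investigator learns of a congenital anomaly in a child conceived later.

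**The concern.** The sponsor asks patients to avoid conception for 90 days after the last dose, but the explicit request to hear about a conception stops at day 30. A site reading Section 9.15 could reasonably take 30 days as the limit.

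At stake is early notice of a late pregnancy. Section 9.15's follow-up to the end of pregnancy depends on someone reporting that pregnancy. Reports that arrive only when an outcome is abnormal leave out the normal outcomes, so there is no denominator.

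The protocol's own nonclinical summary (2.2.3.3) gives some reason to want this information. The embryo-fetal figure is below the maternal one in both species: 3 against 5 mg/kg in rats and 24 against 48 mg/kg in rabbits. The rat sentence does not make clear whether 3 mg/kg is a no-effect level or a toxic dose, but it is the lower figure on either reading.

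**Working it through.** There is no planned figure to reproduce. The check compares the stated windows and then looks for any other rule that fills the difference.

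**Inputs**
- Contraception after last dose: 90 days (Protocol 6.1, criterion 11).
- Pregnancies to be reported to the investigator: up to 30 days after study medication (Protocol 9.15).
- Final visit: 30 ± 7 days after last dose, that is days 23 to 37 (Protocol 8.3.3).

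The two windows start from slightly different wording (completion of study medication, last dose). I treat these as the same day.

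**Difference**
- 90 − 30 = 60 days, namely days 31–90.
- 60 / 90 = 67% of the post-treatment contraception period. This is a share of calendar days, not of pregnancies.
- From the final visit to day 90: 90 − 37 = 53 days to 90 − 23 = 67 days.

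**Does another rule cover days 31–90?**

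| Rule | Does it require a day 31–90 pregnancy to be reported as such? |
|---|---|
| 9.15, investigator to sponsor within 24 hours | Not clearly. It has no day limit of its own, but follows a sentence about pregnancy during the study |
| 9.15, abortion always serious | Only that outcome; 9.3 later narrows reports to related events |
| 9.15 and 9.20, congenital anomaly | Only that outcome, with no stated time limit |
| 9.3, adverse event collection | Does not name pregnancy; after the collection period, related serious events only |
| 8.1.3, pregnancy tests | No; the last is within 30 days after treatment completion |
| 5.6, survival follow-up | No; BTC and STS only, and the listed data are survival status and cause of death |
| SAP | No; it adds no pregnancy follow-up |

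**Partners of male patients.** The contraception rule covers them. The pregnancy-reporting sentences in 9.15 are built around the female patient and do not mention a partner's pregnancy. Only the congenital-anomaly sentence does.

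**If aligned.** With a reporting period equal to the contraception period the protocol already states, the gap is 90 − 90 = 0 days.

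**The case against.** The strongest reply is that the two sentences in 9.15 govern different steps. The 30-day sentence sets what must reach the investigator, while the 24-hour sentence sets what the investigator passes on and carries no day limit. On that reading, a site that hears of a day-60 pregnancy would still send it to the sponsor. This is fair as far as it goes, and nothing tells a site to withhold such a report. But if the 24-hour sentence already reached every later pregnancy, the added 30-day sentence would have little purpose. The text is ambiguous, and nothing obliges the patient to tell the site after day 30.

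A second reply is that the windows do not strictly contradict each other. Contraception is a precaution and reporting is data collection, so a site can comply with both. The 30-day limit also fits the final visit, the last test and general adverse event collection. That stands: this is a mismatch between related rules, not an impossibility.

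A reader might infer three stronger things that the documents do not support:
- **That late pregnancies will go unreported and outcome data will be lost.** Congenital anomalies and related serious events keep a reporting route.
- **That the protocol itself declares days 31–90 a period of fetal risk or exposure.** It states a contraception period and gives no rationale for its length. The nonclinical section says nothing about conception after dosing stops.
- **That the 67% measures missed cases.** It counts days only.

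The consent pages and the Appendix 1 flowchart are not in the text available, so what patients are told about late pregnancies could not be checked.

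**Conclusion.** The mismatch is real and minor. For 60 days the protocol asks patients to avoid conception without any express duty to report a pregnancy as such, so follow-up to the end of that pregnancy is not clearly triggered. The practical loss is mainly prospective notification and follow-up of uncomplicated late pregnancies, or of those the site never hears about.

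The documents give no expected number of pregnancies. That few will occur is an assumption, based on a population with advanced cancer under a contraception requirement.

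The conclusion rests on the ordinary reading of 9.15, in which the 30-day sentence extends a duty otherwise tied to the study period. A broad reading of that period could include survival follow-up, which would help some BTC and STS patients but not Arms B and C. It could also include the continued tumor assessments of patients who stop for reasons other than progression (5.5). Neither reading covers everyone to day 90.

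**What to change.** 1. Reconcile Protocol 6.1 (criterion 11) and 9.15 so that the pregnancy-reporting period is not shorter than the contraception period the protocol sets. The length of that period is for the sponsor to decide.
2. State in 9.15 whether the duty covers pregnancies in partners of male patients, and that the 24-hour report and follow-up to the end of pregnancy apply throughout the reporting period.
3. Align the site safety-reporting instructions and the patient-facing instructions.

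**Cost.** One or two sentences in the protocol, matching edits to the instructions, and slightly more site follow-up. No SAP change is needed. Changing the number alone will not guarantee capture: with no scheduled test after the 30-day point and no common contact after the 30 (±7) day visit, late cases depend largely on self-report. For BTC and STS patients in survival follow-up, the contact every 8 (±2) weeks could carry a pregnancy question at little cost. If that interval runs from the final visit, the first contact falls near day 30 + 56 = 86 (range 23 + 42 = 65 to 37 + 70 = 107).

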9.16 Liver Function Abnormality

The finding of an elevated ALT or AST ($>3 \times$ baseline value) in combination with either an elevated total bilirubin ($>2 \times$ ULN) or clinical jaundice in the absence of cholestasis or other causes of hyperbilirubinemia is considered to be an indicator of severe liver injury; these findings meet the definition for Hy’s Law, and are associated with an increased risk of drug-induced liver injury (DILI). Therefore, investigators must report as an AE the occurrence of either of the following:

- Treatment-emergent ALT or AST $>3 \times$ baseline value in combination with total bilirubin $> 2 \times$ ULN (of which 35% is direct bilirubin)
- Treatment-emergent ALT or AST $>3 \times$ baseline value in combination with clinical jaundice

The most appropriate diagnosis or (if a diagnosis cannot be established) the abnormal laboratory values should be recorded on the Adverse Event CRF and reported to the sponsor

or its designee within 1 working day after learning of the event as an SAE. See [Appendix 7](#) for important additional information.

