	stable or declining, continue with the original dose treatment; If the ALT and/or AST continue to rise significantly, then interrupt surufatinib; resume treatment at a lower dose if transaminase elevation resolves to \leq Grade 1 within 21 days; otherwise discontinue treatment.	
Grade 3: ALT $>5 \times$ ULN or AST $>5 \times$ ULN	Hold surufatinib; resume treatment at the lower dose if resolves to \leq Grade 1 within 21 days; otherwise discontinue treatment.	Check total bilirubin. ^a Provide supportive care and increase the frequency of liver function monitor to twice a week; consult expert if necessary.
Grade 4: ALT $>20 \times$ ULN or AST $>20 \times$ ULN	Discontinue treatment.	Check total bilirubin. ^a Urgent medical intervention indicated.

^a If ALT or AST escalates to 3 times baseline level with bilirubin $>2 \times$ ULN, the biochemical criteria for Hy's Law have been met, surufatinib should be discontinued immediately, and the event should be reported to the sponsor within 24 hours. See [Appendix 7](#) for important additional information.

Table 10 Dose Modification for Hemorrhage

Grade and Definitions	Dose modification	Suggested Actions
Grade 1	None.	Follow up per planned schedule.
Grade 2	Hold surufatinib treatment; Resume at a lower dose if resolves to \leq Grade 1 within 21 days.	Active management.
Grade 3 or higher	Discontinue treatment.	Immediate medical intervention to identify and treat the source of bleeding.

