9.7 Documenting Adverse Events

When documenting an AE or SAE, the preferred medical terminology or concept should be used. Abbreviations and spoken language should be avoided. All AEs (including SAEs) should be recorded in the CRF on the AE page.

Investigators should use correct medical terminology/concepts when recording AEs or SAEs on the CRF. Avoid colloquialisms and abbreviations.

All AEs (including SAEs) would be recorded on the AE CRF, and the check box for "Serious" would be ticked for entries that fit the criteria of serious. The investigator would also complete an SAE report and submit this to the sponsor or its designee within 24 hours of knowledge of the event.

Only one medical concept should be recorded in the event field on the CRF.

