9.18 Expedited Reporting Requirements for Serious Adverse Events

9.18.1 Reporting Requirements for Serious Adverse Events

Investigators will submit reports of all SAEs, regardless of attribution, to the sponsor or its designee within 24 hours of learning of the events.

For initial SAE reports, investigators should record all case details that can be gathered on the SAE report form. Relevant follow-up information should be submitted to the sponsor or its designee as soon as it becomes available and/or upon request.

Any life-threatening (ie, imminent risk of death) or fatal AE that is attributed by the investigator to the investigational product will be telephoned to the Medical Monitor immediately, followed by submission of written case details on the SAE report Form within 24 hours.

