12 OVERSIGHT

12.1 Independent Monitoring

No independent data monitoring is planned for this study. The sponsor will review study safety data on an annual basis, or more frequently, if safety concerns arise.

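### Protocol 9.16 gives investigators 1 working day to report a possible Hy's Law case as an SAE, in conflict with the 24-hour rule in 9.7, 9.18.1 and, for the bilirubin form, Table 9 footnote a

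*Protocol*

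**What the plan says.** Four places in the current protocol set a reporting time that applies to this event.

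- **Section 9.16 (Liver Function Abnormality)** describes two findings: ALT or AST above 3 times baseline with total bilirubin above 2 x ULN, and the same transaminase rise with clinical jaundice. It calls them indicators of severe liver injury and has them reported to the sponsor or its designee "within 1 working day after learning of the event as an SAE". It then refers the reader to Appendix 7.
- **Section 9.18.1** states the general rule: "Investigators will submit reports of all SAEs, regardless of attribution, to the sponsor or its designee within 24 hours of learning of the events". It makes no exception for liver events.
- **Section 9.7** gives the same limit for the SAE report, which the investigator is to "submit this to the sponsor or its designee within 24 hours of knowledge of the event".
- **Section 7.2.3, Table 9 footnote a** covers a transaminase rise to 3 times baseline with bilirubin above 2 x ULN. There, "surufatinib should be discontinued immediately, and the event should be reported to the sponsor within 24 hours".

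All four are in the body of the protocol, not in the amendment history.

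**The concern.** Section 9.16 classes the event as an SAE and then gives it a longer deadline than the protocol allows any SAE. A site looking up what to do with a possible Hy's Law case would naturally go to the section written for it, and could reasonably take its specific deadline as replacing the general one. Nothing in 9.16 points to 9.18.1, so the section does not correct that reading. Over a weekend, a site doing exactly what 9.16 says would breach 9.18.1.

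What is at stake is how soon the sponsor hears of a single case of possible drug-induced liver injury. Hepatic disorders are an identified risk of surufatinib (Section 3.3). The individual report matters because the other oversight is periodic: Section 12.1 plans no independent data monitoring and says "The sponsor will review study safety data on an annual basis, or more frequently, if safety concerns arise", and the sarcoma safety committee in Section 5.4 reviews data after the first 4 patients in each sarcoma cohort have completed at least one cycle.

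**Working it through.** The plan states no figure to reproduce. The check sets the deadlines side by side and then converts the difference into hours.

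**Step 1. Which deadlines apply to which form of the event**

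| Form of the event | 9.16 | 9.7 and 9.18.1 | Table 9 footnote a |
|---|---|---|---|
| Transaminase rise with bilirubin > 2 x ULN | 1 working day | 24 hours | 24 hours, and stop drug |
| Transaminase rise with clinical jaundice | 1 working day | 24 hours | not covered unless bilirubin is also > 2 x ULN |

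Every case that meets the bilirubin form in 9.16 also meets footnote a, because 9.16 asks for slightly more (a rise above, not to, 3 times baseline, and a direct-bilirubin fraction). For that form 9.16 conflicts with three other places. For the jaundice form it conflicts with 9.7 and 9.18.1 only.

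**Step 2. How far apart the two deadlines can be**

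Assumptions: a Monday-to-Friday working week, and a site that uses all the time 9.16 allows. The protocol does not define a working day, so two readings are shown.

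Formula: hours late = (hours from learning of the event to the 9.16 deadline) − 24.

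*Reading 1: the same hour on the next working day.*

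- Friday 17:00, due Monday 17:00: 72 − 24 = 48 hours late.
- Friday 17:00 with Monday a holiday, due Tuesday 17:00: 96 − 24 = 72 hours late.
- Monday to Thursday: 24 − 24 = 0.

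*Reading 2: close of the next working day, taken as 17:00.*

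- Friday 09:00, due Monday 17:00: 80 − 24 = 56 hours late.
- Monday 09:00, due Tuesday 17:00: 32 − 24 = 8 hours late.

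A Friday case in an ordinary week is thus 48 to 56 hours late, or about 2 days. A case early in the week is 0 to 8 hours late.

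**Step 3. What else in the protocol acts on the same case**

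- Dosing: footnote a stops surufatinib immediately for the bilirubin form, whenever the report is sent.
- Gravest cases: under 9.18.1, a life-threatening or fatal AE "attributed by the investigator to the investigational product will be telephoned to the Medical Monitor immediately".

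What remains is a late notice to the sponsor for a case that is not fatal or life-threatening, or that the investigator does not attribute to the drug.

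**The case against.** The strongest reply is that the 24-hour rule already binds. Section 9.18.1 covers all SAEs, 9.16 itself calls the event an SAE, and a site that reports within 24 hours satisfies every section. Every ALT/AST grade in Table 9 also tells the investigator to check bilirubin and carries the marker for footnote a, so someone managing raised transaminases is led to the 24-hour rule. This stands as a reason to rate the point low. It does not remove the conflict: a site may follow the event-specific rule, and doing so over a weekend breaches the general one. The route through footnote a does not help with the jaundice form.

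Some stronger readings are tempting, and the documents do not support them:

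- *The protocol has no 24-hour rule for these cases.* It has one, in 9.7 and 9.18.1, and again in footnote a for the bilirubin form.
- *Patients would stay on drug over the weekend because of the longer deadline.* Section 9.16 governs reporting, not dosing, and footnote a stops drug at once for the bilirubin form.
- *An average delay or a share of affected cases can be given.* Either would depend on an assumed hour of day, an assumed spread of events over the week and an undefined working day. The documents also do not say how many such events to expect.
- *Section 9.16 is wrong to say that* "investigators must report as an AE the occurrence of either of the following". Section 9.7 records every event, serious or not, on the AE page first and then marks it as serious; 9.16 follows that order and ends by calling the event an SAE.
- *Other reporting times in the protocol settle the matter.* The 24 hours for pregnancy in 9.15 and the 48 hours for DLTs in 9.2 concern different events.

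Appendix 7, to which both 9.16 and footnote a refer, was not in the text available for review, so nothing is claimed about any deadline it sets. Its content could not remove the conflict among the four places compared here.

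**Conclusion.** Section 9.16 is wrong as written: it is an internal conflict in a safety-reporting rule, and its severity is minor. Its deadline of 1 working day contradicts the 24 hours in 9.7 and 9.18.1 for both forms of the event, and the 24 hours in Table 9 footnote a for the bilirubin form. The practical size is a Friday case reported on Monday, about 2 days past the protocol's SAE deadline, or about 3 days past it with a Monday holiday. That assumes a Monday-to-Friday week and a site that uses the full time 9.16 allows.

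The existence of the conflict depends on none of these assumptions; only its size does. The consequence is confined to when the sponsor is told. No efficacy result, error rate or sample size changes.

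**What to change.** In 9.16, replace "within 1 working day after learning of the event as an SAE" with: *as an SAE within 24 hours of learning of the event (see Section 9.18.1)*. This aligns 9.16 with the other three places and adds the missing cross-reference.

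The cost is one phrase in one section, by clarification letter or in the next amendment. It needs no new tests, visits or data, and leaves the liver criteria and stopping rules as they are.
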